## LIST OF ABBREVIATIONS

Abbreviation	Definition
AE	Adverse Event
BMI	Body Mass Index
BSL	Baseline
COC	Combined Oral Contraception
CRO	Contract Research Organization
DMP	Delayed/Missed Pill
E2	Estradiol
e-CRF	electronic Case Report Form
EOS	End-Of-Study
FAS	Full Analysis Set
FASM	Full Analysis Set – Cervical Mucus
FASO	Full Analysis Set – Ovarian Activity
FASC	Full Analysis Set – Overall Conception Protection
FSH	Follicle-Stimulating Hormone
ICH	International Conference on Harmonization
IMP	Investigational Medicinal Product
ITT	Intent-To-Treat
LC-MS/MS	Liquid Chromatography with double Mass Spectrometry
LH	Luteinizing Hormone
LNG	Levonorgestrel
NG	Norgestrel
OAS	Ovarian Activity Score
OC	Oral contraceptives
OS (q, a, alp, nlp)	Ovarian Status (quiescence, ovarian activity, ovulation with abnormal luteal phase, ovulation with normal luteal phase)
P4	Progesterone
PD	Pharmacodynamics
PK	Pharmacokinetic(s)
POP	Progestin Only Pill
PP	Per-Protocol
SAF	Safety
SAE	Serious Adverse Event
SAP	Statistical Analysis Plan
T2R-1/T3R-1	Time of treatment intake on the day before delayed intake/missed pill per randomization arm, in treatment period 2/3
TMS	Time of Mucus Scoring
TVUS	TransVaginal Ultrasound
WHO	World Health Organization

## 1.0 INTRODUCTION

This statistical analysis plan (SAP) was developed after review of the 151042-002 study protocol version 1.0 26FEB2018 and case report forms (e-CRFs) version 2.0 06JUN2018, but before any analysis of the data had begun. Detailed information is given to aid in the production of the statistical output and the statistical section of the Final Study Report. This document gives a summary of the protocol and describes the populations that will be analyzed. All subject characteristics and efficacy and safety parameters that will be evaluated, along with the specific statistical methods, are described.

## 2.0 PROTOCOL SUMMARY

### 2.1 Background

Oral contraceptives (OCs) are the most widely used hormonal method of contraception in the United States (US). Combined estrogen-progestin OCs (COCs) are the most frequently-prescribed OCs in the US, while progestin-only pills (POPs) are less frequently prescribed. POPs are mainly prescribed to breastfeeding women or when the use of a COC is contra-indicated.

Opill® (norgestrel (NG) 75 mcg) is a 2nd generation synthetic progestin-only oral contraceptive in the US in 1973 (under the proprietary name Ovrette®) at a daily dose of 75 mcg and first marketed in 1974 in the US. NG is a mixture of two enantiomers, only one of which, levonorgestrel (LNG), being the active form. LNG have been marketed in the US and in Europe for more than 30 years in a wide variety of contraceptive products (including combined and progestin-only oral contraceptives, implant, vaginal ring, intrauterine system and emergency contraceptives).

There are only very few studies assessing the PK of oral NG/LNG for use as POP and no data linking the PK to the pharmacodynamic (PD) action of POPs. In the light of limited PK and PD data on NG and POPs in general that supports the clinical guidance of taking it every day at the same time within a three hour window, this exploratory study aims to determine the PD mechanisms underlying the contraceptive protection of NG 75 mcg. Primarily, the study will evaluate whether these PD mechanisms are impacted by a delayed intake or a missed pill.

### 2.2 Objectives

The primary objectives of the study are:

- to determine the effect of a delayed intake of 6 hours or of a missed pill on cervical mucus score compared to cervical mucus score during reported perfect daily use of norgestrel 75 mcg
- to estimate the duration of the protective effect of cervical mucus after last pill intake of norgestrel 75 mcg during reported perfect use (The protective effect of cervical mucus is considered as present when the score is below or equal 4.)

---

 defined as the day before the delayed intake or the missed pill

The secondary objectives of the study are:

[figure not shown]
- to evaluate and compare the percentage of subjects with a protective cervical mucus score during reported perfect daily use of norgestrel 75 mcg, during a treatment period with a delayed intake of 6 hours and during a treatment period with a missed pill of norgestrel 75 mcg.
- to evaluate and compare the ovarian activity during reported perfect daily use, during a treatment period with a delayed intake of 6 hours and during a treatment period with a missed pill of norgestrel 75 mcg.
- to assess if a combination of cervical mucus score and ovarian status can be considered as a measure of protection from conception during reported perfect daily use, during a treatment period with a delayed intake of 6 hours and during a treatment period with a missed pill of norgestrel 75 mcg.
- to determine levonorgestrel pharmacokinetics after a single dose of norgestrel 75 mcg, at steady state, after a delayed intake and after a missed pill.
- to assess the safety of norgestrel 75 mcg taken daily for 12 weeks.

### 2.3 Design

This is an exploratory, prospective, multi-center, randomized, cross-over study to assess the effect of norgestrel 75 mcg on cervical mucus and ovarian activity during reported perfect daily use and after a delayed intake of 6 hours and after a missed pill.

Women of reproductive age (18-35 years old inclusive) who meet eligibility requirements will be recruited for this study. This study has a screening period of up to 1 month to demonstrate ovulatory status prior to enrollment followed by three 28-day treatment periods (approximately 3 months) and a possible follow-up of 12 days if ovarian activity shows a follicle  $\geq 15$  mm is observed at the end of period 3 and an end of study (EOS) visit within 5 days. During the treatment period 2 the subjects will be randomized into two arms: Arm A will have a delayed pill intake of 6 hours on D42 ( $\pm 3$  days) and Arm B will have a missed pill (24-hour delayed pill intake on D42 ( $\pm 3$  days)). In the next treatment period, these subjects will cross-over meaning Arm A will have a missed pill (24-hour delayed pill intake) on D70 ( $\pm 3$  days) and Arm B will have a delayed pill intake of 6 hours on D70 ( $\pm 3$  days) (see Figure 1 below).

**Figure 1: Design of the Study**

 defined as treatment period 1

## 2.4 Study Endpoints

### 2.4.1 Primary Endpoint

The primary outcomes/endpoints are the changes from baseline (BSL), where baseline is the day before the infringement. Abbreviations for visits are defined in section 3.7.1.

- Delta from BSL to V2R (Day 42±3) = Mucus score at V2R - score at V2R-1 (Day 41±3): change from baseline to 3 (delayed pill period) or 6 hour (missed pill period) after infringement
- Delta from BSL to V2R+1 (Day 43±3) = Mucus score at V2R+1 - score at V2R-1 (Day 41±3): Change from baseline to just before pill intake the day after infringement
- Delta from BSL to V3R (Day 70±3) = Mucus score at V3R - score at V3R-1 (Day 69±3): Change from baseline to 3 (delayed pill period) or 6 hour (missed pill period) after infringement
- Delta from BSL to V3R+1 (Day 71±3) = Score at V3R+1 - score at V3R-1 (Day 69±3): Change from baseline to just before pill intake the day after infringement

The subordinate primary endpoint is the proportions of subjects with “protective effect of cervical mucus” the missed pill period and the delayed pill period for the following categories:

- Full protection by cervical mucus regardless of the use of norgestrel 75 mcg
- Absence of risk increase further to delayed intake
- Absence of risk increase further to missed pill
- Absence of risk increase due to infringement regardless of the type
- Transient risk increase further to delayed intake
- Transient risk increase further to missed pill
- Prolonged risk increase further to delayed intake
- Prolonged risk increase further to missed pill

### 2.4.2 Secondary Endpoints

#### Cervical Mucus

- The percentage of subjects with cervical mucus score ≤ 4, between 5 and 8 (inclusive), and ≥ 9 in reported perfect use period
- The percentage of subjects with cervical mucus score ≤ 4, between 5 and 8 (inclusive), and ≥ 9 in delayed pill intake periods
- The percentage of subjects with cervical mucus score ≤ 4, between 5 and 8 (inclusive), and ≥ 9 in missed pill periods
- The percentage of subjects with cervical mucus score ≤ 4 in all periods

The perfect use period is all visits in period 1 of the study. The worst (meaning highest) cervical mucus score in the period will be used for the analyses.

 see section 3.7.1 for definitions of each risk category

Ovarian Activity

- The percentage of subjects with OSq, OSa, OSalp and OSnlp in reported perfect use period
- The percentage of subjects with OSq, OSa, OSalp and OSnlp in delayed pill intake periods
- The percentage of subjects with OSq, OSa, OSalp and OSnlp in missed pill periods
- The percentage of subjects with OSnlp in all periods

The perfect use period is all visits in period 1 of the study. The worst (meaning most risk of ovulation) ovarian activity category in the period will be used for the analyses.

Conception Protection

The endpoints will be, for each treatment period, the distribution of subjects:

- considered as protected: OSq or OSa or cervical mucus score  $\leq 4$
- considered as at risk of conception: OSalp or OSnlp and cervical mucus score  $\geq 5$
- minimum protection or unlikely to be protected: OSnlp and cervical mucus score  $\geq 9$
- medium protection or likely to be protected: OSnlp and cervical mucus score comprised between 5 and 8 (inclusive) or OSalp and cervical mucus score  $\geq 5$
- maximum protection or highly likely to be protected: OSq or OSa or a cervical mucus score  $\leq 4$

Pharmacokinetics

- PK parameters including C24h, Cmax and AUC

Safety

- incidence of adverse events
- bleeding patterns by cycle

A summary of the **efficacy** objectives and endpoints for the study is below:

Efficacy Objective	Efficacy Endpoint	Statistical Test	Table Number
Effect on cervical mucus score	Mucus score at V2 R - score at V2 R-1 (Day 41±3): change from baseline to 3 (delayed pill period) or 6 hour (missed pill period) after infringement	Repeated measures mixed model	14.2.1
	Mucus score at V2 R+1 - score at V2 R-1 (Day 41±3): Change from baseline to just before pill intake the day after infringement	Repeated measures mixed model	14.2.1
	Mucus score at V3 R - score at V3 R-1 (Day 69±3): Change from baseline to 3 (delayed pill period) or 6 hour (missed pill period) after infringement	Repeated measures mixed model	14.2.1
	Score at V3 R+1 - score at V3 R-1 (Day 69±3): Change from baseline to just before pill intake the day after infringement	Repeated measures mixed model	14.2.1
Duration of the protective effect of cervical mucus	Full protection by cervical mucus regardless of the use of norgestrel 75 mcg	McNemar	14.2.3
	Absence of risk increase further to delayed intake	McNemar	14.2.3

Efficacy Objective	Efficacy Endpoint	Statistical Test	Table Number
	Absence of risk increase further to missed pill	McNemar	14.2.3
	Absence of risk increase due to infringement regardless of the type	McNemar	14.2.3
	Transient risk increase further to delayed intake	McNemar	14.2.3
	Transient risk increase further to missed pill	McNemar	14.2.3
	Prolonged risk increase further to delayed intake	McNemar	14.2.3
	Prolonged risk increase further to missed pill	McNemar	14.2.3
Percentage of subjects with a protective cervical mucus score	The percentage of subjects with cervical mucus score $\leq 4$ , between 5 and 8 (inclusive), and $\geq 9$ in reported perfect use period	McNemar	14.2.6
	The percentage of subjects with cervical mucus score $\leq 4$ , between 5 and 8 (inclusive), and $\geq 9$ in delayed pill intake periods	McNemar	14.2.6
	The percentage of subjects with cervical mucus score $\leq 4$ , between 5 and 8 (inclusive), and $\geq 9$ in missed pill periods	McNemar	14.2.6
	The percentage of subjects with cervical mucus score $\leq 4$ in all periods	McNemar	14.2.6
Ovarian activity	The percentage of subjects with $OS_q$ , $OS_a$ , $OS_{alp}$ and $OS_{nlp}$ in reported perfect use period	McNemar	14.2.9
	The percentage of subjects with $OS_q$ , $OS_a$ , $OS_{alp}$ and $OS_{nlp}$ in delayed pill intake periods	McNemar	14.2.9
	The percentage of subjects with $OS_q$ , $OS_a$ , $OS_{alp}$ and $OS_{nlp}$ in missed pill periods	McNemar	14.2.9
	The percentage of subjects with $OS_{nlp}$ in all periods	McNemar	14.2.9
Combination of cervical mucus score and ovarian status	Percentage of subjects in each period considered as protected: $OS_q$ or $OS_a$ or cervical mucus score $\leq 4$	None	14.2.10
	Percentage of subjects in each period considered as at risk of conception: $OS_{alp}$ or $OS_{nlp}$ and cervical mucus score $\geq 5$	None	14.2.10
	Percentage of subjects in each period with minimum protection or unlikely to be protected: $OS_{nlp}$ and cervical mucus score $\geq 9$	None	14.2.10
	Percentage of subjects in each period with medium protection or likely to be protected: $OS_{nlp}$ and cervical mucus score comprised	None	14.2.10

Efficacy Objective	Efficacy Endpoint	Statistical Test	Table Number
	between 5 and 8 (inclusive) or OS alp and cervical mucus score $\geq 5$		
	Percentage of subjects in each period with maximum protection or highly likely to be protected: OS q or OS a or a cervical mucus score $\leq 4$	None	14.2.10

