depending upon the question of interest because the effect of intake infringement cannot be assessed in these cycles. The assessment of evaluable cycles, the exclusion of cycles from a given analysis and the exclusion of a subject from the FASM/FASO/FASC will be decided in a blinded manner by an independent adjudication committee.

The FASM, FASO and FASC (or evaluable populations) will be used in the primary analysis for assessing the effect of delayed or missed pill on cervical mucus scores and on secondary pharmacodynamic analyses.

Per-protocol (PP) – This population consists of all subjects from the FASM/FASO/FASC without major protocol violation/deviation and with complete cervical mucus and ovarian activity data for all the three treatment periods. Relevant protocol violation/deviation will be defined during the data review. This will include pill intake compliance issues and early ovulation.

The PP population will be used for assessing the efficacy and PK results without missing data and possibly biased data due to protocol violations/deviations. This will be the "cleanest" results for assessing the effect of infringement and the PD effect at the expense of completeness of the set of randomized women and representativeness of the treated population.

The number of subjects in each population will be summarized for all subjects.

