### 3.7.2 Secondary Efficacy Analyses

#### 3.7.2.1 Cervical mucus protection in each type of treatment period

The aim of this secondary objective is to assess the level of cervical mucus protection during reported perfect use, during a treatment period with a delayed pill intake of 6 hours and during a treatment period with a missed pill of norgestrel 75 mcg. The FASM population will be used for the analysis and a sensitivity analysis will be done using ITT and PP.

The time frames are:

- reported perfect use: all the visits of the period 1
- delayed pill intake: all the visits of the period 2 for Arm A and all the visits of period 3 for Arm B.
- missed pill: all the visits of the period 2 for Arm B and all the visits of period 3 for Arm A.

The assessment criterion is the cervical mucus score. The cut off is a cervical mucus score of 4. There is conception protection by cervical mucus if the cervical mucus score is  $\leq 4$ .

The endpoints are:

- The percentage of subjects with cervical mucus score  $\leq 4$ , between 5 and 8, and  $\geq 9$  in reported perfect use period
- The percentage of subjects with cervical mucus score  $\leq 4$ , between 5 and 8, and  $\geq 9$  in delayed pill intake periods
- The percentage of subjects with cervical mucus score  $\leq 4$ , between 5 and 8, and  $\geq 9$  in missed pill periods
- The percentage of subjects with cervical mucus score  $\leq 4$  in all periods

If the cervical mucus was too thick to be collected (and thus a cervical mucus score could not be obtained) the analysis will consider the sample to have good contraception protection and have a cervical mucus score  $\leq 4$ . Otherwise if the cervical mucus score is missing the subject will not be included in the analysis. A period must have at least 7 cervical mucus assessment to be included in the summaries. A stratified McNemar test (stratification on the site, CMH option in SAS) will be used to compare the distribution of cervical mucus scores in the perfect use period to the delayed and missed pill periods (pairwise vs perfect use).

The worst (meaning highest) cervical mucus score in the period will be used for the analyses.

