## **5.0 APPENDICES**

### 5.1 Schedule of Assessments

Study periods	Screening visit	Treatment phase										Follow up(a)	End of study visit
		Treatment period 1	Treatment period 2				Treatment period 3						
Days	-	D1 to D28	D29 to D56				D57 to D84				D85 to D96	Between D85 and D100	
		D1 to D28	D29 to D40 ±3 And D44±3 to D56	D41±3 to D43±3		D57 to D68 ±3 And D72±3 to D84	D69±3 to D71±3						
Visits	V0	V1 1 to V1 2	V2 1 to V2 4				V3 1 to V3 4				V4 1 to V4 2	V4 3	
		Visits twice a week if follicle < 15 mm Visits every other day for a maximum of 6 days if a growing follicle ≥ 15 mm identified upon TVUS(b)	Visits twice a week if follicle < 15 mm Visits every other day for a maximum of 6 days if a growing follicle ≥ 15 mm identified upon TVUS(b)	Delayed/missed pill period Three consecutive days		Visits twice a week if follicle < 15 mm Visits every other day for a maximum of 6 days if a growing follicle ≥ 15 mm identified upon TVUS(b)	Delayed/missed pill period Three consecutive days			Visits every other day for a maximum of 12 days if a growing follicle ≥ 15 mm identified upon TVUS(c)			
				V2 1A	V2 1B	V2 1C		V3 1A	V3 1B	V3 1C			
Informed consent	X												
Inclusion/exclusion criteria	X	X											
Randomisation			X(d)										
Demographics	X												
Medical, surgical and gynecological history	X												
Physical & gynecological examination	X												
Vital signs(e)	X										X		
Laboratory tests	X										X		
Pap smear(f)	X												
STI screening	X												
High-sensitivity urine pregnancy test (β-HCG)		X(g)									X		
Dispensation of study medication (h)		X	X										

Study periods	Screening visit	Treatment phase										Follow up(a)	End of study visit	
		Treatment period 1	Treatment period 2				Treatment period 3							
Days	-	D1 to D28	D29 to D56				D57 to D84				D85 to D96	Between D85 and D100		
		D1 to D28	D29 to D40 ±3 And D44±3 to D56	D41±3 to D43±3		D57 to D68 ±3 And D72±3 to D84		D69±3 to D71±3						
Visits	V0	V1, to V1 y	V2, to V2 y				V3, to V3 y				V4, to V4 y	V4 y		

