- (m) At V11, the mucus analysis will be performed before the 1st study medication intake
- (n) Mucus analysis to be performed at T2/3R-1 +8 h ± 30 min.
- (o) Mucus analysis to be performed at T2/3TR-1 +3h ± 15 min.
- (p) Mucus analysis to be performed at T2/3R-1 +6 h ± 15 min.
- (q) Mucus analysis to be performed within 30 min before study medication intake
- (r) Blood sampling for PK analysis at D1: subjects with even study number at predose, 2 h ± 15 min, 6 h ± 15 min and 12 h ± 30 min post-treatment and subjects with odd study number at 1 h ± 15 min, 4 h ± 15 min , 8 h ± 30 min and 24 h ± 30 min post-treatment

- (s) Blood sampling for steady state during first visit in week 3: subjects with odd numbers at predose, and between 0.5 h and 2h (morning visit), and subject with even numbers between 5 h and 9 h post-treatment (afternoon visit)
- (t) Blood sampling for compliance during 1st visit of weeks 5 and 9 within 30 min of cervical mucus sampling
- (u) Blood sampling for PK analysis at  $T2/3_{R-1} + 8h \pm 30 \text{ min}$
- (v) Blood sampling for PK analysis at  $T2/3_{R-1} + 3h \pm 15 \text{ min}$ ,  $T2/3_{R-1} + 5.5h \pm 15\text{min}$ ,  $T2/3_{R-1} + 7.5h \pm 30\text{min}$
- (w) Blood sampling for PK analysis at  $T2/3_{R-1} + 6h \pm 15\text{min}$
- (x) Blood sampling for PK analysis at  $T2/3_{R-1}$  within 30 min before study medication intake
- (y) No E2, FSH and LH measurements during extra-visits after postovulatory image is observed

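### The worst mucus score under perfect use includes the Day 1 sample taken before the first pill

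*SAP*

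**What the plan says.** The secondary objective in SAP section 2.2 is "to evaluate and compare the percentage of subjects with a protective cervical mucus score during reported perfect daily use of norgestrel 75 mcg", alongside the delayed-intake and missed-pill periods. A footnote there equates perfect daily use with treatment period 1.

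Section 2.4.2 sets the window: "The perfect use period is all visits in period 1 of the study". Section 3.7.2.1 gives the same time frame ("reported perfect use: all the visits of the period 1") and the summary measure: "The worst (meaning highest) cervical mucus score in the period will be used for the analyses". The resulting categories (4 or below, 5–8, 9 or above) are compared pairwise with perfect use by a site-stratified McNemar test. The percentage of women at 4 or below in all periods is also reported.

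The schedule in section 5.1 places V1_1 in treatment period 1 (D1 to D28). Its footnote (m) says that at V1_1 "the mucus analysis will be performed before the 1 st study medication intake".

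The rules that limit what enters the maximum are:
- Mucus too thick to collect counts as 4 or below, and other missing scores drop the subject (section 3.7.2.1).
- There is a minimum count: "A period must have at least 7 cervical mucus assessment to be included in the summaries".
- The adjudication committee can act on cycles and subjects: "the exclusion of cycles from a given analysis and the exclusion of a subject from the FASM/FASO/FASC will be decided in a blinded manner" (section 3.4).

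**The concern.** The endpoint is meant to describe mucus protection while norgestrel is taken daily. At V1_1 no pill has been taken, so that score is an untreated value. A maximum is sensitive to a single high value, so one untreated score of 5 or more makes the woman unprotected under perfect use, whatever her later scores. It also fails her on the all-periods percentage.

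Periods 2 and 3 have no matching untreated sample, so the error falls on the reference side of both comparisons. Taken alone, it can only raise perfect-use non-protection and so shrink or reverse an apparent loss after an infringement. The pre-dose sample also helps a period reach the minimum of 7 assessments, although it carries no information on treatment.

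A second feature of the same endpoint works in the opposite direction. Periods 2 and 3 each contain a "Delayed/missed pill period Three consecutive days" block on top of the twice-weekly visits, so their maximum runs over more samples.

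**Working it through.** **1. Does the text include V1_1?** V1_1 is a period 1 visit (section 5.1). The window is every period 1 visit and the measure is the highest score (sections 2.4.2 and 3.7.2.1). The V1_1 score is pre-dose (footnote m). The rules on thick mucus, missing scores, minimum count and cycle or subject exclusion do not remove a valid pre-dose score. It is included as written.

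**2. The plan's own figure.** The SAP gives no figure for this endpoint. The nearest is in section 2.5: n = 45, difference 14%, discordance 17%, exact power 79.1%. An exact unconditional McNemar test reproduces this at a one-sided 5% level (79.10%). At the two-sided level of section 3.1 the result is 69.5%. That is a separate matter, and only the 14%/17% scenario is used here, as a yardstick.
- Loss only under infringement: (0.17 + 0.14)/2 = 0.155.
- Loss only under perfect use: (0.17 − 0.14)/2 = 0.015.
- Protected in both: 1 − 0.17 = 0.83, taking no woman as unprotected in both.
- If a fraction u scores above 4 pre-dose, independently of on-drug status, the expected difference becomes 0.14 − u(0.155 + 0.83). It is zero at u = 0.14/0.985 = 14.2%.

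Independence puts this at the unfavourable end, and extra visits are ignored. It is a yardstick and not an expected impact.

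**3. Visit counts (derived; the SAP states no totals).** Twice-weekly visits from Day 1 give 8 in 28 days: V1_1 plus 7 on drug. In periods 2 and 3, adding three consecutive days with the infringement day moved over ±3 days gives 10–11 distinct days. A range of 9–11 is used. Follicle-triggered visits are ignored.

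**4. Size under a threshold model (all rates assumed).** Let q be the on-drug chance of a score of 5 or more per visit, u the pre-dose chance, and ρ the within-woman correlation on a latent normal scale with woman effect b. With Φ the normal distribution function and z its quantile:

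F(q, b) = Φ[(z₁₋q − √ρ·b)/√(1−ρ)]

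- Non-protection over k on-drug visits = 1 − E[F(q, b)^k].
- Period 1 as written = 1 − E[F(q, b)^7 · F(u, b)].

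Non-protection in %, with no true effect of infringement:

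| q, ρ | 7 on drug | 10 on drug | As written, u = 5% | 10% | 20% | 40% |
|---|---|---|---|---|---|---|
| 2%, 0.3 | 11.3 | 14.8 | 14.7 | 18.5 | 26.7 | 44.0 |
| 2%, 0.6 | 8.4 | 10.4 | 10.9 | 14.4 | 22.6 | 41.0 |
| 5%, 0.3 | 24.4 | 30.6 | 26.6 | 29.4 | 35.7 | 49.7 |
| 5%, 0.6 | 18.1 | 21.6 | 19.3 | 21.6 | 27.8 | 43.2 |

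Differences in percentage points (from unrounded values, so the last digit can differ from the table):

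| | u = 5% | 10% | 20% | 40% |
|---|---|---|---|---|
| Added by the pre-dose sample | 1.3–3.4 | 3.6–7.2 | 9.7–15 | 25–33 |
| Added if pre-dose and on-drug scores are unrelated | 3.8–4.6 | 7.6–9.1 | 15–18 | 30–37 |
| Fall in the all-periods percentage | 0.4–1.8 | 1.4–4.1 | 4.9–9.7 | 13–26 |
| Net spurious difference as written (10-visit period minus period 1) | −0.5 to +4.0 | −4.1 to +1.2 | −12.2 to −5.0 | −30.6 to −19.1 |

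At u = 2% the addition is 0.3–1.3 points. Out of 45 women, the additions in the first row are about 1 woman at 5%, 2–3 at 10% and 11–15 at 40%.

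Without V1_1, 10 against 7 visits leaves an upward drift of about 2–6 points (9 against 7: 1.4–4.3; 11 against 7: 2.5–8.0).

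**5. The minimum of 7.** With visits missing independently at random (assumed), the binomial chance that period 1 qualifies is:

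| Missing per visit | 7 of 8, as written | 7 of 7, V1_1 dropped | 6 of 7 |
|---|---|---|---|
| 5% | 94% | 70% | 96% |
| 10% | 81% | 48% | 85% |

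Dropping V1_1 while keeping 7 would lose many women, so the minimum has to be restated as well.

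**The case against.** - **The definition is consistent with itself.** The footnote to section 2.2 defines perfect daily use as treatment period 1, so objective and endpoint agree. This is true, but it only repeats the same imprecise window. A sample taken before the first pill is still not one taken under daily use.
- **The committee might deal with it.** Section 5.2 has it review pill intake against mucus scores and agree on scores for each subject, under a separate charter that is not at hand. The charter could hold such a rule. The SAP does not, and the derivation of a tested endpoint belongs there.
- **The net direction is not fixed.** This stands. With the extra visits in periods 2 and 3 counted, the net artefact is mostly positive at a pre-dose rate of 5%, spans zero at 10% and clearly hides a loss only at 20% and above. At 2% and 5%, removing V1_1 alone leaves a larger net artefact than leaving it in. But that offset is accidental and depends on unknown rates, so it is no reason to keep an untreated score.
- **Size and weight.** The study is exploratory, the pre-dose rate is unknown, and the affected analysis is secondary. The plot in Table 14.2.12 and listing 16.2.6.1 will show the V1_1 scores. This limits the importance of the point, but neither display changes the tested classification.

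**Conclusion.** The point holds. As written, an untreated score enters the perfect-use maximum, which is the reference in both McNemar comparisons and part of the all-periods percentage. This follows from the text and rests on no assumption.

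The size does rest on assumptions. The effect is small (0.3–3.4 points) if 2–5% of women score 5 or more pre-dose, and large (25–33 points) if 40% do, given on-drug rates of 2–5% per visit and correlation of 0.3–0.6. The sample taken alone biases towards hiding a loss of protection. The net direction also depends on the opposite drift from extra visits in periods 2 and 3.

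Only the secondary worst-score mucus comparison and the all-periods percentage are affected. The primary and subordinate primary analyses use the day before infringement as baseline and are untouched. The change should be made before analysis.

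**What to change.** In sections 2.4.2 and 3.7.2.1:

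1. State that the pre-dose V1_1 score is excluded from the perfect-use maximum and from the all-periods percentage.
2. Restate the period 1 minimum for on-drug scores, for example at least 6, since only about 7 scheduled on-drug samples remain.
3. State as a limitation that the maximum in periods 2 and 3 runs over more visits than in period 1 and includes visits before the infringement. This belongs with item 1, because dropping V1_1 removes a partial offset to that drift.

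Optionally, add one supportive analysis with matched visit counts: per woman, keep the infringement day and the day after, plus the twice-weekly visits nearest in cycle day to her on-drug period 1 visits, until the counts are equal. In simulation this left a residual drift of −0.6 to +0.1 points, against +2.0 to +6.8 with all 10 visits. A version using twice-weekly visits only would drop the infringement day and the day after, and could not show a brief effect.

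The cost is some wording and one derivation flag, using data already collected and changing no visit. The price is one fewer period 1 sample per woman.
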